3.10.5. Other sensitivity analyses

The main analysis for the primary outcome will be performed also according to the per-protocol principle. The per-protocol population is defined as described in '3.5. Data sets to be analysed'.

A sensitivity analysis will be performed to examine the sensitivity of the results to missing data assumptions. For this sensitivity analysis, a delta-adjustment approach will be applied, with a fixed constant (to be elicited from a panel of experts) added to the values imputed under the standard missing at random procedure (15).

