We do not expect any missing baseline QoL measurements because they must be completed before randomisation and are filled out in a digital manner in which completion is mandatory and entry errors are impossible. Besides, due to the method of scoring, the KCCQ will always provide an Overall Summary Score, based on a mean of the available other summary scores. For the unlikely case where a baseline value is missing, we have taken on the advice of the reviewer and proposed that multiple imputation is also used for these values (page 7, line 22-27).

Regarding the missing QoL measurements at follow up, it is agreed that the assumption that these data are missing at random is a strong assumption, and agree that sensitivity analyses for which these data are assumed to be missing not at random should be performed. We have now specified these in the protocol (page 8, line 3-6).

It is agreed that missing data due to death is not a missing data problem, however particularly for the KCCQ, which is predictive of clinical outcomes including death, excluding patients from the analysis who died is likely to bias the results. Therefore for our primary and sensitivity analyses we would like to retain the patients who died in the analysis. We will ensure that this issue is part of our discussion and keep an eye out for any emerging methodological research that may help to resolve this issue while allowing us to address the research question of interest.

4. The sample size calculation accounts for a 10% drop-out rate, increasing N from 454 subjects to 498 subjects. Can the authors clarify how 498 subjects were obtained? Applying the standard LTF adjustment, one gets around 506 patients (after rounding up).

We thank the reviewer for his/her suggestion and applied the LTF adjustment as suggested. We performed the calculation:  $N = n / (1-(z/100)) \rightarrow N = 454 / (1-(10/100)) = 504.4$ . Therefore, we adjusted the sample size to 506 subjects to maintain an equal distribution of subjects across both study arms (manuscript: page 9, line 12 / DSMB Charter: page 1, page 6, page 10 / Figure 1 and the Visual Take Home Graphic).

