1.3. Contributors to the statistical analysis plan

1.3.1.Roles and responsibilities

Names	Affiliation	Role on study	SAP contribution
[name]	Radboud University Medical Center,	Coordinating	Drafting the statistical
	department of Cardiology	investigator	analysis plan
[name]	Radboud University Medical Center,	Study statistician	Revisions
	department for Health Evidence		
[name]	Radboud University Medical Center,	Coordinating	Revisions
	department of Cardiology	investigator	
[name]	Radboud University Medical Center,	Principal investigator	Revisions
	department of Cardiology		

1.3.2.Approvals

The undersigned have reviewed this plan and approve it as final. They find it to be consistent with the requirements of the protocol as it applies to their respective areas. They also find it to be compliant with ICH-E9 principles and, in particular, confirm that this analysis plan was developed in a completely blinded manner (i.e. without knowledge of the effect of the intervention(s) being assessed).

[name] 18-04-2024 <signature> <date> [name] 17-04-2024 <date> <signature> [name] 18-04-2024 <signature> <date> [name]

[figure not shown]
<signature>

17-04-2024

<date>

2. Study synopsis

The FRESH-UP study is a randomised, controlled, open-label, multicentre trial to investigate the effects of a 3-month period of liberal fluid intake vs fluid restriction (1500 ml/day) on quality of life (QoL) in outpatients with chronic heart failure (HF).

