2.6. Sample size

Sample size calculation was performed with the software package G*Power 3.1.7 and performed as previously described methods for repeated measures ANCOVA analysis, using baseline QoL as a covariate (1).

For our sample size calculation, a correlation of 0.88 between baseline and follow-up KCCQ-OSS was assumed (2). Furthermore, a follow-up KCCQ-OSS of 66.25 with a standard deviation of 20 was assumed for liberal fluid intake group (3-7). Next, we assume a 2.5-point difference in KCCQ-OSS follow-up scores at 3 months between both randomisation groups (3-7). To test this difference at a p-value of 0.05 and power of 80%, we need a total of 454 evaluable patients. Anticipating a drop-out rate of 10% we aim to enrol 506 patients.

To interpret the clinical relevance of a mean difference of 2.5 points in KCCQ score, it is important to differentiate between differences in scores on a patient level or group level. Based on previous validation studies on a patient level, a change of 5, 10 and 20 points in KCCQ-OSS follow-up scores are considered small, moderate-to-large and large-to-very large clinical important changes respectively (8, 9). Moreover, even smaller changes are possibly associated with clinically important improvements or deteriorations (10). However, a mean difference on randomisation group level is not directly comparable with the clinically important changes on a patient level. Randomisation group means reflect many different outcomes amongst patients, as in each randomisation group patient's clinical status will improve, deteriorate or remain stable.

In view of the above, it is illustrative to look at the results of previous landmark trials which demonstrated positive effects on clinical outcome for the studied interventions, which are now part of guideline-directed medical therapy.

For example, in the PARADIGM-HF (sacubitril/valsartan versus enalapril), the KCCQ-OSS mean difference was 1.27 points, while the proportion of clinically important improvements was greater and the proportion of deterioration was lower for sacubitril/valsartan group compared to the enalapril group (35% versus 33% and 27% versus 31%, respectively) (7).

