3.10. Analysis of the primary outcome

3.10.1. Main analysis

The difference between the two treatment arms in QoL after 3 months, as assessed with KCCQ-OSS, will be tested with the use of an ANCOVA analysis, using baseline QoL as a covariate. The difference will be presented as the average treatment effect for liberal fluid – restricted fluid arm. The estimated difference will be presented with a point estimate and 95% confidence interval. A p-value of <0.05 will be considered significant.

For the primary analysis, the intention-to-treat principle will be applied.

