3.10.4. Treatment of missing data

In the unlikely case that any baseline scores on the KCCQ-OSS are missing, they will first be multiply imputed using imputations drawn from the distribution of the full study population.

Following this, a multiple imputation model will be specified separately by treatment arm and will include baseline and 3-month KCCQ-OSS as well as any auxiliary variables that are considered to be associated with the outcome or with the probability of missing the 3-month KCCQ scores. For the imputation procedure, m = 50 imputed datasets and the missing 3-month KCCQ scores will be imputed using predictive mean matching, type 1 and with k = 5 nearest neighbours specified (14). In the case of any missing data on the selected auxiliary variables, a fully conditional specification imputation approach will be specified with the imputation model for each variable defined according to the variable type.

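### The SAP's only missing-not-at-random check adds one fixed constant to the imputed scores without stating its allocation by arm, sign, range or a tipping point

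*SAP*

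**What the plan says.** SAP 3.10.4 imputes missing 3-month KCCQ-OSS values under missing at random (MAR): "a multiple imputation model will be specified separately by treatment arm", with predictive mean matching and 50 imputed datasets. SAP 3.10.5 then plans two sensitivity analyses. One is per-protocol, which does not test the MAR assumption. The other is a delta adjustment, "with a fixed constant (to be elicited from a panel of experts) added to the values imputed under the standard missing at random procedure". Nothing more is said about the constant: no arm, sign, range, tipping point or date of elicitation.

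In the Protocol document, the reply to major concern 3 accepts that MAR is a strong assumption and that "sensitivity analyses for which these data are assumed to be missing not at random should be performed". It points to page 8 of a text that is not in the package, so this point concerns the SAP only.

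On the amount of missing data, SAP 2.6 gives one overall figure: "Anticipating a drop-out rate of 10% we aim to enrol 506 patients". The only remark by arm is in the Protocol document, in the reply to major concern 6. It describes drop-out as very low in the control group and so far absent in the intervention group, and it gives no rates.

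**The concern.** SAP section 2 states: "The FRESH-UP study is a randomised, controlled, open-label, multicentre trial". The primary outcome is patient-reported. If liberal intake looks better, readers will ask whether that depends on drop-outs in one arm doing worse than MAR predicts. A delta adjustment can answer this only if the constant is allowed to differ between arms.

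The SAP leaves that open. A constant added equally to both arms largely cancels out of the arm difference when the missing shares are similar. The same constant in one arm does not cancel. The same data and the same elicited value can therefore support opposite conclusions, depending on an allocation that the SAP does not state. Under SAP 3.4 the analysis after database lock is done with knowledge of the randomised groups, so the allocation is better fixed before then.

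**Working it through.** **Inputs from SAP 2.6 and 3.10.1.** Difference 2.5, SD 20, baseline to follow-up correlation 0.88, power 80%, 454 evaluable, 506 enrolled (253 per arm). Significance rule: "A p-value of <0.05 will be considered significant", taken as two-sided because a 95% confidence interval is planned.

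**Assumptions.** Missing shares by arm (pL liberal, pR restriction) and the size of the constant (δ) are not in the documents. I use 2% to 12% missing per arm and δ up to 20 points in size. SAP 2.6 says that "a change of 5, 10 and 20 points in KCCQ-OSS follow-up scores are considered small, moderate-to-large and large-to-very large" changes at patient level.

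**The plan's own figure.** Residual variance = 400 × (1 − 0.88²) = 90.24, SD 9.50. Patients per arm = 2 × 90.24 × (1.960 + 0.842)² / 2.5² = 226.7, so 227 per arm and 454 in total. Then 454 / 0.9 = 504.4, so 505, or 506 for equal arms. Both figures reproduce.

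**Formulas.**
- Shift of the arm difference = δL × pL − δR × pR. With one common constant this is δ × (pL − pR).
- Variance = 90.24 × [1/(253(1−pL)) + 1/(253(1−pR))] + δL² pL(1−pL)/253 + δR² pR(1−pR)/253.

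**Equal missingness, 10% per arm, observed 2.5.**
- MAR: variance 2 × 90.24/227.7 = 0.793, SE 0.890. Differences above 1.96 × 0.890 = 1.74 are significant.
- Common −10: shift 0. Variance 0.793 + 2 × 100 × 0.09/253 = 0.864, SE 0.929. Result 2.5 (95% CI 0.68 to 4.32).
- Liberal-only −10: shift −1.0. Variance 0.793 + 100 × 0.09/253 = 0.828, SE 0.910. Result 1.5 (−0.28 to 3.28).

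**Tipping points.** For a common constant at equal missingness, solve d = 1.96 × SE(δ). For liberal-only, solve d + δp = 1.96 × SE(δ). Here d is the observed difference.

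| Missing per arm | Observed d | Common constant | Liberal-only |
|---|---|---|---|
| 10% | 2.5 | −34.2 | −7.3 |
| 5% | 2.5 | −48.3 | −15.1 |
| 2% | 2.5 | −76.2 | −35.9 |
| 10% | 2.0 | −18.7 | −2.5 |
| 10% | 1.8 | −8.4 | −0.5 |

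A restriction-only constant is the mirror image of liberal-only, with the sign reversed. Scores are not truncated to 0–100, so the largest values mean only that the result does not tip within any realistic shift.

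**Unequal missingness, common −10, observed 2.5.**
- 12% liberal, 8% restriction: shift −10 × 0.04 = −0.4. Result 2.1 (0.28 to 3.92).
- 8% liberal, 12% restriction: shift −10 × (−0.04) = +0.4. Result 2.9 (1.08 to 4.72). The negative constant now favours liberal intake.

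**Low missingness.** At 2% per arm, liberal-only −20 gives 2.5 − 0.4 = 2.1 with SE 0.871 (0.39 to 3.81), still significant.

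**Simulation check.** 400 trials of 506 patients per scenario, true difference 2.5, imputation by arm, ANCOVA and Rubin's rules. It used a normal imputation model with 20 imputations, a simplification of the SAP's method. The figures are the share of MAR-significant results that lose significance.

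| Missing, liberal/restriction | Constant | Common | Liberal-only |
|---|---|---|---|
| 10% / 10% | −10 | 3.1% | 52.2% |
| 10% / 10% | −20 | 10.0% | 91.6% |
| 12% / 8% | −10 | 25.2% | 65.7% |
| 8% / 12% | −10 | 0% | 35.7% |

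A further 300 simulated trials using predictive mean matching by arm with 50 imputations gave SEs of 0.891 (MAR) and 0.929 (common −10) at 10% per arm, matching the formula.

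**The case against.** A reader might infer that the SAP plans one constant for both arms and that the check can therefore hardly fail. The documents do not support that. SAP 3.10.5 does not say that the constant is common. The values it modifies are imputed by arm, so an arm-specific constant also fits the text, and the expert panel could settle the allocation. Nor is a common constant toothless. At 10% missing per arm it tips an observed 2.0 at −18.7 and an observed 1.8 at −8.4, both within 20 points. It also moves the estimate when missingness differs between arms.

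Three further objections have weight. A single expert-elicited constant is a legitimate prespecified analysis. The text cited in the reply to major concern 3 is not available and may say more. Missingness may also prove too low to matter: at 2% per arm, neither allocation overturns a 2.5-point result within 20 points. The remark on drop-out by arm even suggests that the restriction arm could have more missing scores. It was made while the trial was running, answers a question about cross-over and gives no rates, so it is only a hint.

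What remains is the omission. Elicitation can supply the size of the constant, but the SAP does not ask the panel for an allocation, sign or range, and the conclusion can depend on them.

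**Conclusion.** The point holds as under-specification, not as proof of a faulty check. If the constant is common, the check is weak when missingness is similar: for an observed 2.5 at 10% missing per arm, it tips at about −34, against about −7.3 for liberal-only. It is less weak nearer the threshold or with unequal missingness. If more restriction-arm scores are missing, a common negative constant moves the estimate towards liberal intake (2.9 at 8% versus 12% and −10), which is why the sign matters too.

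These sizes rest on the SAP's planning values and on assumed missing shares by arm. The primary estimate, its test and the type I error are unaffected. This is a cheap improvement to a supporting analysis.

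**What to change.** In SAP 3.10.5, replace the single constant with separate constants δL and δR, added to the MAR-imputed KCCQ-OSS values of the liberal and restriction arms. Set the grid before database lock and include the elicited value. An example is −20 to +20 in steps of 5, taking the SAP's own 20-point benchmark as the limit. Cover liberal-only, restriction-only and equal shifts. Report the single-arm constant at which the 95% CI changes between excluding and including 0, or state that this is not reached within the grid. Keep the primary MAR analysis as it is.

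The cost is a few sentences in the SAP and a few reruns on the same 50 imputed datasets, with no new method. The downside is a few more results to report and interpret. If missingness is low, the tipping point would let the sponsor show that the result is robust.

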3.11. Analysis of the secondary outcomes

For the secondary parameters thirst distress, as assessed with the TDS-HF, and QoL at 3 months after randomisation, as assessed with the KCCQ-CSS, each of the KCCQ domains and the EQ-5D-5L, a similar approach as for the primary study parameters will be adopted.

The difference between groups in proportion of patients with clinically meaningful changes (defined as a difference of 5 points compared to baseline) in KCCQ-OSS and KCCQ-CSS (8, 10) and the percentage of events (death, all-cause hospitalisations, the need for iv-loop diuretics and acute kidney injury) will be tested with Chi-square or Fisher exact test, whichever appropriate. The

difference in between groups patient reported fluid intake will be analysed with a Students' t test or Mann-Whitney U test, whichever appropriate.

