3.10.2. Adjusted analyses

Not applicable.

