Appendix 1: Proposed tables and figures

All tables and figures are drafts and will not necessarily be included in the final papers in this form.

1. Study disposition figure

2. Baseline characteristics table

	Total (N = ***)	Fluid restriction (N = ***)	Liberal fluid intake (N = ***)
Age, years			
Male			
White†			
Quality of life			
KCCQ-OSS			
TDS-HF			
EQ-5D-5L			
NYHA functional class			
II			
III			
LVEF			
%			
HFrEF			
HFmrEF			
HFpEF			
Pathogenesis HF			
Ischemic			
Dilating			
Hypertension			
Valvular			
Drug-induced Other			
Unknown			
HF duration, years			
Fluid management Fluid restriction of 1L			
Fluid restriction of 1.5L			
Fluid restriction of 1.5 to 2L			
Fluid restriction of 1.5 to 2.			
Liberal fluid intake			
Other			
HF treatment			
ACEi or ARB			
ARNI			
β-blocker			
Digoxin			
MRA			
SGLT2i			
Loop diuretics			
Thiazides			
GDMT score‡			
ICD			
CRT			

Medical history

Atrial fibrillation or flutter

BMI, kg/m²

COPD

DM

Hypertension

Currently smoking

Laboratory results

Haemoglobin, mmol/l

Sodium, mmol/l

Potassium, mmol/l

Urea, mmol/l

eGFR, ml/min/1.73m²

Nt-proBNP, pg/ml

Osmolality, mosm/kg

3. Outcomes

Table: 'Primary and secondary outcomes.'

	Fluid restriction (N = ***)	Liberal fluid intake (N = ***)	P value
Primary outcome			
KCCQ-OSS			
Key secondary outcome			
TDS-HF			
Other secondary outcome			
KCCQ-CSS			
KCCQ-TSS			
KCCQ-PLS			
KCCQ-QoL			
KCCQ-SBS			
KCCQ-SES			
KCCQ-SFS			
KCCQ-SLS			
KCCQ-SSS			
KCCQ-OSS (-5 to +5)			
KCCQ-OSS (-5 or less)			
KCCQ-OSS (+5 or more)			
EQ-5D-5L			
Reported fluid intake			
Safety			
Death			
All-cause hospitalisation			
IV-loop diuretics usage			
Composite of the above			
Acute kidney injury†			
Values are mean ± SD or median (int	erquartile range)		

alues are mean ± SD or median (interquartile range)

EQ-5D-5L = European Quality of Life Five Dimensions Five Levels questionnaire; KCCQ = Kansas City Cardiomyopathy Questionnaire; -CSS = Clinical Summary Score; -TSS = Total Symptom Score; -OSS = Overall Summary Score; -PLS = Physical Limitation Score; -QoL = Quality of Life; -SBS = Symptom Burden Score; -SES = Self-Efficacy Score; -SFS = Symptom Frequency Score; -SLS = Social Limitation Score; -SSS = Symptom Stability Score; IV = intravenous; TDS-HF = Thirst Distress Scale for patients with HF;

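### The 5-point KCCQ responder outcomes are tested by a valid but inefficient unadjusted chi-square; most of the recoverable power lies in the order of the categories, little in baseline adjustment

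*SAP*

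**What the plan says.** For the primary outcome, SAP section 3.10.1 states that the KCCQ-OSS difference at 3 months "will be tested with the use of an ANCOVA analysis, using baseline QoL as a covariate". Section 3.11 extends a similar approach to TDS-HF, KCCQ-CSS, the KCCQ domains and EQ-5D-5L.

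The responder outcomes are handled differently. A meaningful change in KCCQ-OSS or KCCQ-CSS is "defined as a difference of 5 points compared to baseline", and the proportions "will be tested with Chi-square or Fisher exact test, whichever appropriate". No covariate is named, the direction of the change is not given, and nothing is said about using the imputed datasets of section 3.10.4.

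The draft outcome table in Appendix 1 splits KCCQ-OSS change into three rows: -5 or less, -5 to +5, and a last row that begins "KCCQ-OSS (+5 or more". Section 3.3 makes secondary endpoints other than the key one supportive, without multiplicity correction. No power is claimed for the responder outcomes.

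**The concern.** Baseline KCCQ is complete before randomisation (SAP section 2.5) and is already the covariate in the primary model, so leaving it out of the responder analysis saves nothing. The chance of gaining 5 points depends on the starting score, through regression to the mean and the ceiling at 100. The three drafted categories are also ordered from worse to better, and no planned test uses that order.

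The endpoint has some weight despite its supportive status. SAP section 2.6 defends a 2.5-point mean difference by pointing to the shares of patients who improved or deteriorated in earlier trials, and expects the same difference here to matter for individual patients. The responder outcome is the trial's own look at that expectation. If its power is low, a true 2.5-point effect will often come with a non-significant responder result, which could be misread as no benefit at patient level.

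**Working it through.** **Inputs from SAP section 2.6.** "a correlation of 0.88 between baseline and follow-up KCCQ-OSS was assumed"; "a follow-up KCCQ-OSS of 66.25 with a standard deviation of 20 was assumed for liberal fluid intake group"; "we assume a 2.5-point difference in KCCQ-OSS follow-up scores at 3 months between both randomisation groups"; two-sided 0.05 (the section gives 0.05 only, and two-sided reproduces its figure); 80% power; 454 evaluable, hence 227 per arm.

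**Assumptions not in the documents.** Baseline SD 20; baseline mean 63.75 (66.25 − 2.5), with 75 also tried; normal scores, clipped to 0-100 in the simulations.

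**1. The plan's own figure.** Residual SD = 20 × √(1 − 0.88²) = 9.50. n per arm = 2 × (1.960 + 0.842)² × 9.50² / 2.5² ≈ 226.7, so 227, or 454 in total. Then 454 / 0.9 = 504.4, which becomes 506 when rounded up to an even number. Both figures are reproduced.

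**2. How much baseline says about change.**
- SD of change = 20 × √(2 × 0.12) = 9.80.
- Correlation of change with baseline = −√(0.12 / 2) = −0.245, so baseline explains 0.245² = 6% of the variance of change.
- With no treatment effect, expected change is +2.4 at 1 SD below the baseline mean and −2.4 at 1 SD above, with residual SD 9.50. The chance of gaining at least 5 is 1 − Φ(2.6 / 9.50) = 39% and 1 − Φ(7.4 / 9.50) = 22%.
- Share with baseline above 95: 1 − Φ((95 − 63.75) / 20) = about 6%. These patients cannot gain 5 points.

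**3. Responder rates and chi-square power in closed form, without clipping.**
- Improvement: 1 − Φ(5 / 9.80) = 30.5% against 1 − Φ(2.5 / 9.80) = 39.9%.
- Deterioration: Φ(−5 / 9.80) = 30.5% against Φ(−7.5 / 9.80) = 22.2%.
- For improvement, the pooled proportion is 0.352 and the SE is √(2 × 0.352 × 0.648 / 227) = 0.0448. Power = Φ(0.0944 / 0.0448 − 1.96) ≈ 56%. For deterioration it is 52%.

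**4. Simulated power** (2.5-point effect, 227 per arm, clipped scores; 3,000 trials per scenario, Monte Carlo SE √(0.25 / 3000) = 0.9 points; centre not modelled). Ranges show repeat runs, one of them with 800 trials.

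| Analysis | r 0.88, mean 63.75 | r 0.88, mean 75 | r 0.70, mean 63.75 |
|---|---|---|---|
| Chi-square, improved or not | 53% | 46-47% | 25-27% |
| Logistic with baseline, improved or not | 55-56% | 52% | 29% |
| Chi-square, three categories | 56-57% | 53% | 25% |
| Ordinal, no baseline | 65-67% | 63% | 33% |
| Ordinal with baseline | 68-70% | 66% | 37% |

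The ordinal figures in the first column come from proportional-odds models, an unadjusted trend test (the 65%) and a linear-score trend analysis with baseline (the 70%). For deterioration of 5 or more at r 0.88 and mean 63.75, chi-square gives 51% and logistic with baseline 53%.

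**5. Splitting the gain at r 0.88, mean 63.75.** In the 3,000-trial run, power goes from 53% (binary chi-square) to 67% (ordinal, no baseline) to 69% (ordinal with baseline). The order adds about 14 points and baseline about 2.

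**6. Size under no effect.** Binary chi-square 5.7-5.8%, logistic with baseline 5.6%, three-category chi-square 5.3%, proportional odds 5.8%, and 5.7% with baseline.

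**The case against.** The strongest reply is that nothing here is wrong. The declared endpoint is a proportion, and a test of proportions answers it directly. It holds its size, no decision rests on it, and the efficient baseline-adjusted analysis is already the primary one. The raw percentages also compare directly with those cited from earlier trials in SAP section 2.6, which a conditional odds ratio does not. All of this stands, and it is why the ordinal model should sit beside the proportions and not replace them. The proportional-odds model also brings an assumption that the planned test does not need.

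Some stronger readings are tempting, and the documents do not support them:
- **That baseline strongly determines who changes by 5 points.** The 0.88 links baseline to the follow-up score. Subtracting baseline removes most of its influence and leaves 6% of the variance of change. A loss of about 10 points from omitting baseline (49% against 59%) appeared only with correlation 0.5, baseline mean 75 and a 5-point effect, far from the plan's inputs.
- **That chance baseline imbalance makes the test invalid.** Under randomisation the test keeps its size, as step 6 shows.
- **That the plan specifies a three-category test that ignores order.** Section 3.11 specifies no such test. The Appendix 1 tables are labelled drafts, and their rows can be read as separate proportions.
- **That section 3.10.2, with its entry "Not applicable", rules out adjustment here.** It sits under the primary outcome and says nothing about the responder analysis.

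**Conclusion.** The concern holds as a point of efficiency on a supportive endpoint, not as an error. On the plan's inputs the planned test has about 53% power for improvement of 5 points or more. Baseline adjustment alone adds about 2 to 3 points. An ordinal analysis with baseline reaches about 68-70%, and most of that difference comes from the order of the categories. With a true 2.5-point effect, the planned test would miss significance nearly half the time (100% − 53% = 47%).

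These figures rest on the assumed baseline mean and SD, normal scores clipped at the scale limits, full data on 227 per arm, and a uniform shift of 2.5 points. The last of these suits a proportional-odds model; an effect confined to one direction would change the gain. At correlation 0.70 all power figures fall (25-27% for chi-square against 37% for ordinal with baseline), but the ranking of these two is unchanged.

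**What to change.** In section 3.11:
1. State that improvement (gain of 5 or more) and deterioration (loss of 5 or more) are separate outcomes for KCCQ-OSS and for KCCQ-CSS, so that a change of exactly 5 falls in one category only. The draft rows overlap at that value.
2. Analyse each by logistic regression with the matching baseline KCCQ score as covariate, plus centre because randomisation is stratified by it. Report a standardised risk difference with 95% CI beside the raw percentages.
3. Add one prespecified proportional-odds model on the three ordered categories (5 or more worse, in between, 5 or more better) with the same covariates. Check the proportional-odds assumption and show the two separate cut-point results beside the common odds ratio.
4. For KCCQ-OSS, derive the categories within the 50 imputed datasets of section 3.10.4. That model names KCCQ-OSS only, so for KCCQ-CSS impute in the same way with CSS in the model.

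No new data are needed. The cost is some SAP wording and a little more analysis work. The downside is a common odds ratio, which is less direct than a percentage and must be read beside the raw figures. The benefit of adding centre was not simulated, and the power figures above do not depend on it.
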